7.3 Center Pooling

This is a multi-center clinical study, with standardization of subject enrollment, data entry and Adverse Event reporting. All investigational sites will follow the requirements of a common protocol, data collection procedures and forms. Upon justifications, data from all sites will be pooled for analysis.

Analyses to justify pooling will include the following:

Data Pooling Across Sites

Poolability across sites will be assessed using logistic regression model on the primary outcome. The model will include “Responsive: Yes/No” as response variable, and BIS, Site, BIS*Site interaction as exploratory variables. Sites with fewer than five subjects will be combined based on the order from smallest to largest. A P-value of 0.15 or less is considered statistically significant for the evaluation (FDA preferred).

If the sites are found to be significantly heterogeneous with respect to the primary outcome, additional analyses will be conducted to assess differences between sites in baseline and procedural variables that might explain differences in the primary outcome.

Data Pooling of Stage 1 and Stage 2

The study consists of two stages: first 10 subjects (stage 1), and then followed by 20 additional subjects (stage 2). Although no differences will be expected across the two stages, statistical testing will be performed to ensure the 2-stage data can be pooled for analysis. The testing will be based on the logistic regression model with binary “Responsive: Yes/No” as response variable, BIS, Stage indicator (X), BIS*X interaction as exploratory variables.

In case significant differences are present across the two stages, simply pooling data may not be valid. In this case, an alternative strategy will be used for statistical evaluation. Stage 1 data will be utilized as prior, which will be integrated into stage 2 data using the Bayesian Data Integration. More specifically, power prior and discounting function will be used to accommodate the difference across the two stages. Technical details can be found in the Appendix.

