From the above formula, we see that α_0 weights the historical data relative to the likelihood of the current data, and thus the parameter α_0 controls the influence of the historical data on $L(\theta|D)$. The parameter α_0 can be interpreted as a precision parameter for the historical data. Since D_0 is historical data, it is unnatural in practical applications to weight the historical data more than the current data; thus it is scientifically sound to restrict the range of α_0 to be between 0 and 1, that is, $0 \leq \alpha_0 \leq 1$. Setting $\alpha_0 = 1$ corresponds to the update of $\pi_0(\theta)$ using the Bayes theorem. That is, with $\alpha_0 = 1$ corresponds to the posterior distribution of θ based on the historical data D_0 . When $\alpha_0 = 0$, the prior does not depend on the historical data; in this case, $\pi(\theta|D_0, \alpha_0 = 0) = \pi_0(\theta)$. Thus, $\alpha_0 = 0$ is equivalent to a prior specification without incorporation of historical data. Therefore, the approach can be viewed as a generalization of the usual Bayesian update of $\pi_0(\theta)$. The parameter α_0 allows to control the influence of the historical data on the current study. Such control is important in cases where there is heterogeneity between the previous and current studies.

Since the power prior is essentially a likelihood function raised to a power, it shares all the properties that likelihood functions have, and therefore has several advantages over other non-likelihood-based priors. Due to its validity and ease of interpretation, the power prior approach has been widely adopted in practical applications and is commonly seen in medical device regulatory submissions.

[BIS] Statistical Analysis Plan

Revision [\[x\]](#)

Page 15 of 20

Form

Medtronic

B. Primary Efficacy Endpoint

In this study, the primary efficacy endpoint is the BIS₅₀, defined as the BIS™ value at which 50% of subjects are unresponsive at given drug concentrations. The BIS™ is a variable derived from the electroencephalograph (EEG) that has been reported to have the ability to measure the hypnotic component of the anesthetic state. It is a dimensionless number from 0 to 100, and decreasing values indicate more sedation and hypnosis. The MOAA/S scales and BIS™ value will be assessed and recorded when the subject is awake and at different drug concentrations.

The dose-response relationship will be estimated using the logistic model. The model is written as follows:

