$$P = \frac{e^{a+bX}}{1 + e^{a+bX}}$$

where P is the probability of “unresponsive”, X is the explanatory variable (BIS™ value or anesthetic agent concentration on the log scale), and a & b are corresponding model parameters.

In the context of the dose-response model, let θ represents the target BIS™ value on the log scale. Let $D = \{y_1\}$ and $D_0 = \{y_0\}$ represent the current data and prior data respectively. The parameter estimation will be carried out based on the posterior distribution (upon normalization):

$$\pi(\theta|D, D_0, \widehat{\alpha}_0) \propto L(\theta|D) L(\theta|D_0)^{\widehat{\alpha}_0} \pi_0(\theta)$$

where the notation $\widehat{\alpha}_0$ is used to denote that the estimate of α_0 based on the observed data. Of note that the estimate depends on the current data (D) and prior data (D_0). In conjunction with a pre-specified decision rule controlling the prior data weight, the estimate of $\widehat{\alpha}_0$ represents a measure of similarity between the current data and prior data. Alternatively, in the absence of $\widehat{\alpha}_0$, i.e., full weight would be given to the prior data.

C. Statistical Analysis

The Bayesian power prior with discounting function will be used to estimate the target parameter and determine $\widehat{\alpha}_0$, the strength of the prior data used to support the current data. Of note $\widehat{\alpha}_0$ ranges from 0 to 1, where 1 means that 100% of the prior data is used and 0 means that no prior data is used. Before beginning the current study, an initial value is chosen for $\widehat{\alpha}_0$, and let's call this value α_{max} . This α_{max} value is the maximum strength that the prior data can receive. For this study, we intend to use the same protocol and enrollment criteria for the prior and current studies, and therefore believe that a value of $\alpha_{max} = 1$ is appropriate.

The study data will be analyzed using the power prior method along with discounting function. The method will discount α_{max} to an appropriate value $\widehat{\alpha}_0$ where $\widehat{\alpha}_0 \leq \alpha_{max}$. This discounting scale is based on the discounting function which will be discussed in detail in the next section.

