Under the adaptive procedure, if the current study data diverges from the prior data, the discounting function will discount the strength of the prior data. Alternatively, if the prior and current study data agree, there will be no or minimal penalty from the discounting function, thus a large amount of data information would be integrated into current data for statistical inferences.

The primary analysis set consists of all evaluable subjects and will be used for the primary analysis. The per-protocol set will be used for supportive analysis.

D. Discounting Function Estimation Method

The method of power prior discounting function is comprised of four steps: **Compare, Discount, Combine, and Estimate**. Details in each step are presented below.

Compare:

We start by stochastically comparing current data vs prior data as follows.

For each study group, we separately fit the model to the combined prior and current data:

$$H(p_i) = \beta_0 + \beta_1 I(i \in \text{prior}) + \beta_2 d_i + \varepsilon_i, \quad \varepsilon_i \sim N(0, \sigma^2),$$

where H is the inverse logit function, p_i is the probability of target response, d_i is the dose concentration (log scale), and the indication function $I(i \in \text{prior}) = 1$ if the subject is from the prior data, and 0 otherwise. With a flat prior on each parameter, we estimate the posterior probability that $\beta_1 > 0$ by first computing the parameter, using Monte Carlo sampling

$$p^* = P[\beta_1 > 0 \mid D, D_0].$$

Having calculated the parameter for each group, we use the transformation:

$$p = \begin{cases} 2p^*, & p^* \leq 0.5 \\ 2(1 - p^*), & p^* > 0.5 \end{cases}$$

Now, under this transformation, if p is close to 0, there is a high probability that the current data and prior data come from different populations and discounting should be applied to reduce the influence of the prior. On the other hand, if p is close to 1, there is a high probability that the current data and prior data are from similar populations and minimal discounting should be applied.

Discount:

[figure not shown]
Let discount α_{max} based on the value of p from the **Compare** step and the discounting function $F(p)$,

$$\widehat{\alpha_0} = \alpha_{max} F(p),$$

where $F(p)$ is a function between 0 and 1. A two-sided Weibull function will be utilized as follows:

$$F(p) = 1 - e^{-(p/\lambda)^k}.$$

For this study, we will be using a shape parameter of $k = 3$ and a scale parameter of $\lambda = 0.5$ (illustrated below).

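### The Stage 1 weight for BIS50 is set by a concentration-response comparison that contains no BIS term, and the stage test that triggers it has no stated level

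*SAP*

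**What the plan says.** - **Target.** SAP Appendix I.B: "In this study, the primary efficacy endpoint is the BIS₅₀, defined as the BIS™ value at which 50% of subjects are unresponsive". The parameter theta in the posterior "represents the target BIS™ value on the log scale".
- **Purpose of the discount.** Appendix I.C: "if the current study data diverges from the prior data, the discounting function will discount the strength of the prior data".
- **How the weight is set.** The Compare step in Appendix I.D regresses response on an intercept, a Stage 1 indicator (coefficient beta_1) and d_i, which "is the dose concentration (log scale), and the indication function" defines. The posterior probability that beta_1 exceeds 0 is folded into a two-sided p. The Stage 1 likelihood for theta is then raised to the power F(p), a Weibull function with shape 3 and scale 0.5.
- **When it is used.** SAP 7.3 tests stage poolability with "BIS, Stage indicator (X), BIS*X interaction as exploratory variables". If the stages differ significantly, "In this case, an alternative strategy will be used for statistical evaluation", namely the power prior. SAP 7.5 repeats that stage poolability is tested. Appendix I.C states no condition: "The study data will be analyzed using the power prior method along with discounting function".
- **Level.** The only level in SAP 7.3 is in the paragraph on pooling across sites: "A P-value of 0.15 or less is considered statistically significant for the evaluation". The stage paragraph gives none and does not say which term, or which joint test, decides.

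**The concern.** The weight is meant to measure how well the two stages agree on BIS50. As written it measures how well they agree on concentration-response. The two can separate: if BIS readings at a given clinical state move between stages while the concentrations at which subjects lose responsiveness do not, BIS50 moves and the Compare model sees nothing. Detection and remedy then use different covariates. SAP 7.3 can flag a BIS50 difference and pass the data to a step that sets the weight without reference to BIS.

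At stake is the stated protection against pooling unlike stages for the primary parameter, in the one relation the study exists to estimate. The undefined trigger adds a second problem. Whether Stage 1 is fully pooled or discounted, and therefore the effective sample size claimed in SAP section 6, depends on a rule the SAP leaves open.

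**Working it through.** **1. The plan's own sample size.** SAP section 6: difference 0.15, SD 0.25, two-sided 0.05, power 80%. A one-sample t-test gives n = 24 with power 80.4%, so the figure reproduces. Section 6 then takes 10 × 0.8 + 20 = 28 as the smallest effective size.

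**2. What the Compare model can see.** Its terms are the intercept, the stage indicator and log concentration. BIS is absent, so p and F(p) do not change when BIS readings change at fixed concentration and response. This follows from the equation and needs no simulation.

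**3. The discount function when the stages agree.** F(p) = 1 − exp(−(p/0.5)³). With p uniform, mean F is 0.5535. F reaches 0.8 only if p ≥ 0.5 × (−ln 0.2)^(1/3) = 0.586, which has probability 0.414.

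**4. Size from the Appendix I.F inputs.** 10 and 20 subjects; BIS50 60, ratio 1.15, so 69 in Stage 2 (a shift of 9); SD 25% of 60 = 15; normal subject values. The standardised shift is z = 9/(15 × √(1/10 + 1/20)) = 1.55, or 1.47 if the Stage 2 SD is 25% of 69 = 17.25. The table prints a prior SD of 1.25, which is not 25% of 60, so that value was run as well. Pull is 69 minus the mean combined BIS50, with Stage 1 weighted by F (2 million draws).

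| Basis of the weight | Mean weight | Pull toward Stage 1 |
|---|---|---|
| Stage difference in BIS50, SD 15 or 17.25 | 0.22–0.24 | 0.19–0.21 points |
| Same, prior SD 1.25 as printed | 0.04–0.07 | 0.03–0.06 points |
| A contrast the shift does not move | 0.55 | 1.8 points |
| Full pooling | 1 | 9 × 10/30 = 3.0 points |

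The planned precision is ±15% of 60 = ±9 points. None of these weights matches the mean of 90.4% reported in Appendix I.F. A plug-in calculation with subject-level SDs comes close: z = 9/√(15² + 17.25²) = 0.39, p = 0.69, F = 0.93 (0.91 with SD 15 in both stages). The reported figure may therefore rest on a different comparison.

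**5. The Compare step on simulated trials.** The documents give no concentration-response or BIS curves, so these are assumptions: sevoflurane steps 0.2–5%, population EC50 1%, BIS falling from 95 to 25, BIS noise SD 4, and five combinations of between-subject spread; 1,500 trials per cell. Stage 2 BIS50 is raised by 9 points with concentration-response unchanged.

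| Quantity | Log concentration (as written) | BIS as covariate |
|---|---|---|
| Weight, no shift | 0.40–0.55 | 0.31–0.54 |
| Weight, shift | 0.40–0.55 | 0.02–0.25 |
| Weight, shift flagged by the 7.3 test at 0.05 | 0.40–0.57 | 0.00–0.06 |
| Pull toward Stage 1 (points) | 1.2–1.7 | 0.01–0.20 |

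The ranges span ordinary logistic, subject-robust and random-intercept fits; the pull uses the first two. A second simulation with different curves agrees. Multiplying Stage 2 BIS by 1.00 to 1.30 leaves the weight as written at 0.47–0.50, while the BIS-based weight falls from 0.56 to 0.000.

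If BIS50 moves because responsiveness itself moves, the weight as written drops to 0.02–0.18, so that kind of shift is caught.

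**6. The trigger.** In the second simulation a 10% BIS shift triggers the 7.3 stage test (2 df) in 55% of trials at level 0.05 and 75% at 0.15. With agreeing stages and a calibrated test on the same contrast:

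- always discounting: 20 + 10 × 0.5535 = 25.5 effective subjects on average;
- discounting only if significant at 0.05: mean F given p < 0.05 is 0.0002, so 0.95 × 30 + 0.05 × 20.0 = 29.5;
- discounting only if significant at 0.15: mean F given p < 0.15 is 0.0067, so 0.85 × 30 + 0.15 × 20.07 = 28.5.

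The 28 in section 6 is therefore not a minimum under any of these rules: the average falls below it in the first, and flagged trials fall to about 20 in the other two.

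**The case against.** **Possible labelling slip.** The SAP uses dose-response language for the BIS relation, its general logistic model allows X to be BIS or log concentration, and the Appendix I.F inputs are BIS50 values. BIS may have been intended. But the Compare step names concentration only, and a programmer following the text would code that.

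**Narrow case, small effect.** The gap needs BIS50 to move without concentration-response moving. The SAP expects no stage difference, and the documents point to no cause for one of this kind. The 7.3 test contains BIS and flags the 9-point shift in 67–83% of the simulated trials at 0.05. The pull is under 2 points, and once the power prior is used Stage 1 carries roughly half weight on average. All of this stands and limits the severity. It does not repair the rule, because the weight stays blind after the test has flagged the shift.

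**The trigger may be clear enough.** SAP 7.3 calls the power prior an alternative strategy, and Appendix I.C can be read as describing that method, not as setting a rival rule. That reading is reasonable, so this is an ambiguity and not a firm contradiction. The missing level is real.

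**Sample size.** Every expected effective size above exceeds 24. The 7.3 test fitted as ordinary logistic ignores repeated measures and flags 8–37% of agreeing trials; even at 37% with Stage 1 dropped, 0.63 × 30 + 0.37 × 20 = 26.3. No average loss of power is shown. Only the claim that 28 is a minimum fails.

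**Conclusion.** The concern holds. The Stage 1 weight for BIS50 comes from a model without BIS, so it does not respond to a stage difference confined to the BIS-response relation. That contradicts the appendix's own account of what the discount does. This conclusion rests on the printed equation alone.

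The consequence is modest. For a 15% shift in BIS50 the combined estimate is pulled about 1.2 to 1.8 points toward Stage 1, against about 0.2 or less with a BIS-based weight and a planned precision of ±9. The upper figure uses the Appendix I.F inputs with normal subject values; the rest of the range depends on assumed curves and is illustrative. Shifts that also move concentration-response are mostly caught.

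The unstated stage-test level and the unclear scope of the power prior are a lesser omission, but they leave the Stage 1 retention in section 6 undetermined. This should be corrected before the final analysis; it does not threaten the study.

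**What to change.** 1. In Appendix I.D, for BIS50 and BIS95, replace d_i in the Compare model with the BIS value, or base p directly on the stage difference in BIS50. Allow for repeated measures within subject. Keep log concentration for EC50 only. A BIS-by-stage term is optional.
2. In SAP 7.3 and Appendix I.C, state one rule for when the power prior applies (always, or only after a significant stage test), with the level and the deciding term. The choice is the sponsor's.
3. Rerun Appendix I.F with the corrected step, state which comparison produced the 90.4%, and reconcile the printed prior SD of 1.25 with a CV of 25%. Then restate the 80% retention and the effective size of 28 in section 6 for the chosen rule.

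**Cost.** One equation, one sentence with a level, matching code and a simulation rerun; no change to conduct or data collection. There are three trade-offs:

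- The retention figure may come out lower.
- A BIS-based Compare step discounts a responsiveness shift somewhat less when between-subject BIS spread is wide (weight 0.02–0.32 against 0.02–0.18).
- If the 7.3 test remains the gate and uses nearly the same contrast, the discount becomes almost all-or-nothing. Flagged regimens drop to about 20 effective subjects, where the section 6 one-mean test has power of about 72%. The sponsor should weigh this when choosing the rule.

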**Combine:**

Using the power prior method and discounting factor $\widehat{\alpha}_0$, one can combine the prior and current data together using the Bayesian method to construct the posterior distribution for the parameters of interest.

[figure not shown]
Estimate:

The posterior distribution from the combined prior and current data is used to make statistical inferences:

$$\hat{\pi}(\theta | D, D_0, \widehat{\alpha}_0) \propto L(\theta | D) L(\theta | D_0)^{\widehat{\alpha}_0} \pi_0(\theta)$$

[figure not shown]
where the notation $\widehat{\alpha}_0$ is used to denote that the estimate of α_0 depends on the current data, prior data, and the Weibull shape and scale parameters. In conjunction with a prespecified decision rule controlling the prior data weight, the estimate of $\widehat{\alpha}_0$ represents a measure of similarity between current and prior data. Alternatively, in the absence of $\widehat{\alpha}_0$, full weight would be given to the prior data.

For illustrative purposes, the blue dashed line in the figure below is an example of the integrated estimate from current data (black) and prior data (red).

E. Illustration of Discounting Function Scenarios

The Figure below shows how the discounting function operates with hypothetical data sets

The panels in this figure can be interpreted as follows:

- **Top panel:** The current data is very similar to the prior. The discounting function allows for full strength of the prior. The posterior (final estimate) is a balance between the prior and current study.
- **Middle panel:** The current data is similar to the prior. The discounting function penalty is moderate, resulting in a prior effective sample size of 17 out of a max of 50. Because the agreement is reasonable, the posterior (final estimate) is similar to both the prior and current study.
- **Bottom panel:** The current data shows lower performance than the prior. The discounting function produces a substantial penalty resulting in no weight to the prior. The posterior (final estimate) is essentially the same as the current study.

F. Simulation of Operating Characteristics

Extensive simulations were performed to assess operating characteristics for the statistical analysis. We used 10k trial simulations to estimate the power and 10k simulations to estimate the operating characteristics. The following

[BIS] Statistical Analysis Plan

Revision [\[x\]](#)

Page 19 of 20

Form

[figure not shown]
Medtronic

table summarizes the assumptions that were made for the primary endpoint simulations, and the figure summarizes the operating characteristics for the discounting parameter.

Table: Simulation Assumptions for Primary Endpoint Analysis

Assumptions	Values
Prior Subjects	10
Current Subjects	20
BIS ₅₀ Value (Mean)	60
Prior Data BIS ₅₀ Value (CV%)	25%
Prior Data BIS ₅₀ Value (SD)	1.25
Current Data BIS ₅₀ Value (CV%)	25%
BIS ₅₀ Value Ratio (Current vs Prior)	1.15
Weibull Discounting Function Parameters	shape: $k = 3$, scale: $\lambda = 0.5$

Simulation results are summarized in the following figure. As expected, there is good distributional overlapping between the prior and current data. The amount of prior data integrated to the current data is quantified by the discounting parameter, which has a mean value of 90.4% with corresponding 95% credible interval (53.1%, 99.9%). Overall, the variations between prior and current data have been taken into account and valid statistical inferences can be made.

Figure: Posterior distribution of the discounting parameter (10k simulations)

G. References

- [1] <http://mdic.org/computer-modeling/virtual-patients/>
